| 2.0 | 13 October 2023 | 
Updated section 2.3.1, item (2) to remove “all-cause” and “stroke-related mortality” from the endpoint description to remain consistent with protocol. 90-day mortality is the primary safety endpoint collected in case report forms. “All-cause” and “stroke-related” mortality categories are not collected separately.Updated section 3.1.1 to add clarification baseline definition for blood work, ECG, CXR. Baseline definition added for infarct volume.Updated section 3.3.1 to state that Disposition will be summarized by Enrolled Population. Removed “Screened subjects” as a disposition category because all screened subjects are not recorded in electronic data capture.Updated section 3.4.2 subsection (1) to include dichotomized mRS counts and percentages and include bar charts for mRS.Updated section 3.4.2 subsection (2) to include additional details for infarct volume summarization.Updated section 3.4.2 subsection (3) to include NIHSS spaghetti plots.Updated section 3.4.2 subsection (4) to designate subjects with worsening of stroke.Removed previous text under section 3.4.4. Added subsection 3.4.4.1 for analysis of mRS, 3.4.4.2 for correlation analysis of infarction volume and clinical outcomes, and 3.4.4.4 for analyses with additional covariates (post-hoc).Updated section 3.5.1 to add “Study drug related TESAEs” as an overview category. TEAE occurrence by month updated to |

| Version | Version Date | Description of Changes |
|---------|------------------|---|
| | | 
display occurrence category by week for the first month and monthly thereafter.
 
 • Updated section 3.5.3 to add Table 6 for derived timepoints and Table 7 with vital signs range • Updated section 3.5.5 to include language on derived timepoints. • Updated section 6/4 to clarify primary safety endpoint a s90-day mortality. • Global change: Updated treatment name as RNS60 1.0 mL/kg/h • Included additional reference FDA (2018) in Appendix B. |

| MedDRA | Medical Dictionary for Regulatory Activities |
| MI | Multiple Imputation |
| MNAR | Missing Not at Random |
| MRI | Magnetic Resonance Imaging |
| mRS | Modified Rankin Scale |
| n | Number of Observations |
| NCCT | Non-contrast Computed Tomography Scan |
| NIHSS | National Institutes of Health Stroke Scale |
| PD | Protocol Deviation |
| PP | Per Protocol |
| QTcF | QT interval corrected for heart rate using Fridericia's correction |
| RNA | Ribonucleic Acid |
| RSPL | Residual Pseudo-Likelihood with a Subject-specific expansion |
| SAE | Serious Adverse Event |

| Abbreviation | Definition |
|---------------------|--|
| SAP | Statistical Analysis Plan |
| SDTM | Study Data Tabulation Model |
| TEAE | Treatment-emergent adverse event |
| TESAE | Treatment-emergent serious adverse event |
| TFL | Tables, Figures and Listings |
| TIA | Transient Ischemic Attack |
| VAS | Visual Analogue Scale |
| WHO | World Health Organization |

1 INTRODUCTION

The purpose of this statistical analysis plan (SAP) is to provide a description of the statistical methods to be implemented for the analysis of data from the study with protocol number 06.5.1.H1 dated 09 May 2022 (version 2.4). The SAP will be finalized prior to database lock. Any future addendum to the SAP (if applicable) will be referenced in the Clinical Study Report (CSR).

The SAP will be considered as the governing document and in case of any differences between this SAP and the study protocol, the SAP will supersede the protocol.

2 STUDY OVERVIEW

2.1 Study Objectives

2.1.1 *Primary Objective*

The primary objective is to determine the safety of RNS60 in adult subjects (aged 18 years or older) with large vessel occlusion (LVO) and acute ischemic stroke (AIS) based on serious adverse events (SAEs) and 90-day mortality. To be eligible for this trial, subjects must have sudden onset of focal neurological symptoms within 24 hours prior to randomization consistent with an ischemic stroke. Symptoms must be persistent and present at the time of enrollment.

2.1.2 *Secondary Objectives*

The secondary objectives are to evaluate the efficacy of RNS60 in the following outcomes:

1. Reducing global disability (as measured using the Modified Rankin Scale [mRS] at 90 days)
2. Decrease in infarct volume (as defined by imaging at 48 hours)
3. Improving neurological outcome (as measured using the National Institutes of Health Stroke Scale [NIHSS] at 24 hours)
4. Reducing worsening of stroke, defined as progression, or hemorrhagic transformation, of the index stroke as documented by medical imaging that results in:
 - (a) a life-threatening situation requiring intervention, and/or
 - (b) increased disability as determined by a ≥ 4 -point increase from lowest NIHSS pre decline, and/or
 - (c) death by 48 hours or during hospital admission.
5. Reducing functional dependence (as defined by mean Barthel Index (BI) at Day 90)
6. Improving health-related quality of life, as measured by the EuroQol health-related quality of life (EQ-5D-5L) at Day 90

These outcomes will be assessed in the following hierarchical order (to control for the overall Type I error rate): first between high-dose RNS60 (1.0 mL/kg/h RNS60) compared to placebo, then both low and high dose RNS60 combined compared to placebo, and then between low-dose RNS60 (0.5 mL/kg/h RNS60) compared to placebo. In the analyses of efficacy, the combined-dose inference will be done within the statistical models by averaging the results in the two active doses and comparing to placebo. (This is in contrast to performing a separate

analysis in which subjects on active dose are treated as a single treatment arm.) The exception to this approach is the non-parametric analysis in Section 3.4.4.1, where the data in the two active arms are combined into a single group to be compared to placebo.

2.1.3 *Attributes of the Estimands*

The attributes of the main estimand (target of estimation), used for the primary analysis of the highest ranked efficacy endpoint (modified Rankin Scale (mRS) score) are defined below. Although the primary objective of this study is related to safety, analysis of the efficacy endpoints (secondary objectives of the study) will be based on a pre-defined hierarchy and therefore, an estimand is defined.

- The **population** is defined as the intent-to-treat study population (see Section 3.2.3).
- The corresponding **variable** to be obtained for each subject required to address the scientific question is disability based on the mRS score at Day 90. The mRS will be evaluated as a binary outcome (0-2, 3-6).
- The **population level summary** considered in this study is the odds ratio between RNS60 1.0 mL/kg/h and placebo 1.0 mL/kg/h.
- The **treatments** to be compared are RNS60 1.0 mL/kg/h and placebo 1.0 mL/kg/h. The treatments will be compared according to the randomized groups, regardless of the treatment that was actually received. In accordance with the treatment policy principle, all available data will be used in the analysis, regardless of e.g., premature discontinuation of study medication or administration of any concomitant treatment.
- The **intercurrent events** (ICEs) considered as potentially impacting results and/or interpretation are:
 - Premature discontinuation of study treatment
 - Death
 - Coronavirus Disease 2019 (COVID-19) pandemic related events (assessments that were missed due to COVID-19).

For the data that are missing due to premature discontinuation of study treatment, an assumption of Missing At Random (MAR) will be made. Sensitivity analyses will be conducted using an assumption of Missing Not At Random (MNAR). No specific imputation will be done for these missing data, because the likelihood-based analysis approach can manage subjects with incomplete data under the assumption of MAR.

For the data that are missing due to COVID-19, an assumption of MAR will be made for all analyses, both primary and sensitivity analyses.

For the mRS, NIHSS and BI endpoints death is included as part of the scoring, so no imputation of these endpoints is required for subjects who die. Similarly, for the worsening of stroke endpoint, death represents a worsening. For the infarct progression end point, death will be represented by a missing value.

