Safety Outcomes	
Safety outcomes include:
 
 • Serious adverse events (SAEs) to Day 90 • 90-day mortality 
Additional Safety outcomes include:
 
 • Adverse events (AEs) to Day 90 • Drug administration discontinuations due to AEs • Baseline and 48-h vital signs • Baseline and 48-h electrocardiogram • Baseline and 48-h chest X-ray (CXR)
Efficacy Outcomes	
The efficacy outcomes (secondary) are:
 
 1) Mean modified Rankin Scale (mRS) at Day 90 2) 90-day mortality 3) Mean NIHSS at 24h and Day 90 4) Proportion of patients exhibiting a worsening of their index stroke.* 5) Mean Barthel Index (BI) at Day 90 relative to pre-stroke BI. 
*Worsening of stroke is defined as progression, or hemorrhagic transformation of the index stroke, as documented by brain imaging, and that is (a) life-threatening requiring intervention and/or (b) results in increased disability as gauged by a \geq 4-point increase from lowest NIHSS score pre decline and/or (c) results in death.
 
Tertiary/exploratory outcomes include:
 
 1) Infarct progression/regression as measured by MRI brain imaging. 2) Health-related quality of life, as measured by the 5-level EuroQoL 5D index (EQ-5D-5L) at Day 90.

Number of Participants	
An initial target of 100 male and female participants with LVO AIS and who are selected for endovascular revascularization will be enrolled.
 
Attrition factors include death from stroke but not treatment (10%), symptoms of fluid overload (20%) and early discharge (5%).

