3 TRIAL OBJECTIVES

3.1 Objectives

Table 3-1: Objectives and Outcomes

Objectives	Outcomes
Primary – Safety	
To determine the safety based on SAEs	Proportion of participants with SAEs to Day 90
90-day mortality	Proportion of participants alive at Day 90
Secondary – Efficacy	
Reducing global disability in participants with AIS	Mean mRS score
Reducing mortality rate	Median or proportion of death on survival curve
Improving neurological outcome	Mean NIHSS score at discharge
Reducing worsening of stroke	See 3.1.2
Reducing functional dependence	Mean BI at Day 90
Tertiary/Exploratory	
Decreasing infarct volume	Volume of stroke as measured by MRI brain imaging
Improving health related quality of life	EQ-5D-5L at Day 90

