3.2.2 Secondary Efficacy Outcomes

Secondary outcomes include:

- 1) The mean mRS score at Day 90, where a lower score is better.
- 2) A reduction in mortality rate, as defined by a lower event rate on a Kaplan Meier survival curve
- 3) The mean NIHSS score post randomization, where a lower score is better
- 4) The proportion of patients with worsening of stroke over the 90-day study period
- 5) The mean BI at Day 90

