Worsening of stroke is defined as progression, or hemorrhagic transformation of the index stroke, as documented by brain imaging, which is (a) life-threatening requiring intervention and/or (b) results in increased disability as gauged by a ≥ 4-point increase from lowest National Institutes of Health Stroke Scale (NIHSS) pre decline and/or (c) results in death.

5) Barthel Index at Day 90.

The BI is an index of functional independence. Its values range from 0 to 100, with higher scores indicating greater independence.

Table 4. Scales and score range in BI

| Item | Score range |
|-----------------------------------|-------------|
| Feeding | 0-10 |
| Bathing | 0-5 |
| Grooming | 0-5 |
| Dressing | 0-10 |
| Bowels | 0-10 |
| Bladder | 0-10 |
| Toilet use | 0-10 |
| Transfers (bed to chair and back) | 0-15 |
| Mobility (on level surfaces) | 0-15 |
| Stairs | 0-10 |

Item scores vary in increments of 5 points.

6) Health-related quality of life, as measured by the EuroQol health-related quality of life (EQ-5D-5L) at Day 90.

EQ-5D-5L is developed by EuroQol Research Foundation and is a generic instrument for measuring and describing health-related quality of life.

It consists of two elements, a 5-item questionnaire and an EQ-Visual Analogue Scale (VAS). Both elements are interviewer administered by study staff.

EQ-5D-5L is a version that further improves the sensitivity of EQ-5D-3L, provides respondents with a wider range of options to describe their health and is comprised of five response levels to five different dimensions.

- **5-Item Questionnaire:** The questionnaire provides a simple descriptive profile of health state. The questionnaire comprises 5 dimensions (mobility, self-care, usual activities, pain/discomfort, anxiety/depression) and each dimension has 5 response levels (1-no problems, 2-slight problems, 3-moderate problems, 4-severe problems,

5-unable to/extreme problems). The resulting 5-digit code corresponds to the response of each dimension of the health state. For instance, 11111 and 55555 indicate the best health condition and the worst health condition, respectively.

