In addition to the primary time point of each endpoint (as defined below), all other applicable time points will be compared as well and interpreted in an exploratory manner.

In these analyses, testing the combined-dose versus placebo will be done within the statistical models by averaging the results in the two active doses and comparing to placebo. (This is in contrast to performing a separate analysis in which subjects on active dose are treated as a single treatment arm.)

Generalized linear mixed models will be implemented for the analyses of disability based on mRS, infarct volume, NIHSS at 24 hours, worsening of stroke, and Barthel Index. NIHSS will be analyzed on the recorded scale of measurements and the treatment groups' Least Squares (LS) means, corresponding 95% confidence intervals (CIs), and LS mean differences will be reported. Disability based on mRS, worsening of stroke, and Barthel Index are dichotomized endpoints that will be analyzed on the logit scale of measurement. The resulting LS means and confidence intervals will be back-transformed to probabilities, and differences in least squares means will be reported as odds ratios. Infarct volume will be analyzed as log-normally distributed, and descriptive statistics will be geometric means where between-group comparisons will be reported as ratios of geometric means. Covariates baseline NIHSS and ASPECTS binary factors for efficacy analysis will use baseline values from the Electronic Data Caputre.

1. Modified Rankin Scale (mRS) score:

The effect of treatment on global disability at Day 90 will be examined by comparing the proportion of subjects who had disability (Yes or No) between the three treatments (RNS60 1.0 mL/kg/h, RNS60 0.5 mL/kg/h, and placebo 1.0 mL/kg/h) using generalized linear mixed modeling (GLM) using residual pseudo-likelihood with a subject-specific expansion(RSPL) assuming a binary outcome (0-2=0, 3-6=1). Covariates include the Age, baseline NIHSS, and ASPECTS binary factors used for block urn randomization and baseline (pre-morbid) mRS, baseline occlusion location, study site, baseline perfusion status, and log of baseline infarct volume. Treatment, visit day, and interaction of treatment and visit day are included as categorical fixed effects.

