The effect of treatment on functional independence at Day 90 will be examined by comparing subjects achieving functional independence (Barthel Index score ≥ 95 as compared to < 95) where subjects having a score ≥ 95 on the Barthel Index Score at Day 90 will be deemed to have achieved functional independence, and those scoring < 95 at Day 90 will be deemed to have failed to achieve functional independence.

The proportion of subjects who achieved functional independence (BI score ≥ 95 vs. < 95) at Day 90 will be compared between the three treatments (RNS60 1.0 mL/kg/h, RNS60 0.5 mL/kg/h, and placebo 1.0 mL/kg/h) using generalized linear mixed modeling using RSPL assuming a binary outcome ($< 95 = 0$, $\geq 95 = 1$). Covariates include the Age, baseline NIHSS, and ASPECTS binary factors used for block urn randomization and baseline BI total, log of baseline infarct volume, baseline perfusion status, baseline occlusion location, and study site. Treatment, visit day, and interaction of treatment and visit day are included as categorical fixed effects.

Sensitivity analysis of BI will be performed in a similar way to the primary analysis using the GLM approach with RSPL assuming a binary outcome ($<95=0$, $\geq 95=1$) where any missing value of BI will be imputed as functional independence not achieved (coded as 0).

3.4.3 Sensitivity Analysis for Secondary Efficacy Endpoints with Dichotomous Data for Baseline Collaterals

For each of the secondary efficacy endpoints described in section 3.4.2, additional sensitivity analysis will be performed using the GLM analysis approach where baseline collaterals will also be included in the model. For subjects with a baseline collateral score, the score will be converted to baseline collateral status. Baseline collaterals dichotomization will use the following conversion approach:

Dichotomization A (main): where a baseline collateral score of 0-2 indicates Baseline collateral status = Absent, and a baseline collateral score of 3-5 indicates Baseline collateral status = Present

Dichotomization B: where a baseline collateral score of 0 indicates Baseline collateral status = Absent, and a baseline collateral score of 1-5 indicates Baseline collateral status = Present.

Dichotomization C: where a baseline collateral score of 0-1 indicates Baseline collateral status = Absent, and a baseline collateral score of 2-5 indicates Baseline collateral status = Present.

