6.4 Changes from Protocol-Specified Statistical Analyses

The protocol specifies ITT population as all randomized subjects. This SAP clarifies that ITT population will include all randomized subjects who received study drug. ITT population will exclude subjects who were randomized and did not receive study drug.

There are no significant changes from protocol-specified statistical analysis apart from specifying the type of analysis to be used and further defining endpoints. The SAP will be considered as the governing document and in case of any differences between this SAP and the study protocol, the SAP will supersede the protocol.

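### SAP 2.1.2 (5) and the protocol define functional dependence as mean Barthel Index at Day 90, but the SAP's only between-arm Barthel comparison is ≥95 versus <95

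*SAP*

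**What the plan says.** **Objective and outcome.** SAP 2.1.2 (5) reads "Reducing functional dependence (as defined by mean Barthel Index (BI) at Day 90". Protocol Table 3-1 has "Mean BI at Day 90" and protocol 3.2.2 (5) has "The mean BI at Day 90". The protocol synopsis differs slightly: "Mean Barthel Index (BI) at Day 90 relative to pre-stroke BI". SAP 2.3.2 (5) gives neither a mean nor a cut-point. It names the index at Day 90 and adds "Its values range from 0 to 100, with higher scores indicating greater independence".

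**Analysis.** SAP 3.4.2 states: "Disability based on mRS, worsening of stroke, and Barthel Index are dichotomized endpoints that will be analyzed on the logit scale of measurement". Its Barthel subsection examines the treatment effect by "comparing subjects achieving functional independence (Barthel Index score ≥ 95 as compared to < 95" at Day 90, in a binary mixed model. The sensitivity analysis there keeps the same split and counts missing values as not independent. These results fill items 5 (high dose), 10 (combined) and 15 (low dose) of the hierarchy.

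**What it replaces.** Protocol 9.3.3 models BI over its 0-100 range with a binomial distribution and plans Dunnett-corrected pairwise comparisons at Day 90. SAP section 1 says that the SAP prevails where the two documents differ.

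**Disclosure.** SAP 6.4 describes the redefinition of the ITT population, then says "There are no significant changes from protocol-specified statistical analysis" apart from specifying the type of analysis and further defining endpoints. BI is not mentioned there.

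**The concern.** The objective is a mean and the test placed under it is a proportion above a cut. A patient whose score would be 85 rather than 40 because of treatment contributes nothing to the ranked comparison. Both scores are below 95.

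The precedence clause does not settle this, because the mismatch lies inside the SAP, between 2.1.2 (5) and 3.4.2 (5). A reader of the study report would find an odds ratio listed under an objective worded as a mean.

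It also bears on the trial's declared use. There is no power calculation, and protocol 9.3.3 says the efficacy measures are examined to give effect sizes for a later, powered trial. For the outcome the protocol names, the SAP plans no adjusted mean difference and no interval.

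**Working it through.** The documents give no BI distribution, effect size, SD or power, so there is no figure of theirs to reproduce. The check is a comparison of the text plus two illustrations on assumed inputs.

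**1. Where BI appears in the SAP**

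| SAP place | Quantity | Between-arm comparison? |
|---|---|---|
| 2.1.2 (5) | mean at Day 90 | objective only |
| 2.3.2 (5) | index at Day 90, 0-100 | endpoint name only |
| 3.4.2, items 5, 10, 15 | proportion ≥95 | yes |
| 3.4.2 (5), sensitivity | proportion ≥95, missing = not achieved | yes |
| 3.4.3 | same model plus collateral status | yes, still ≥95 |
| 3.4.4.2 | full score, Spearman correlation with infarct volume | no |
| 3.1.4 | general rule: mean and SD for continuous data | no; BI not named |

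No row compares mean BI between arms. By contrast, mRS is also dichotomised for its ranked test, but 3.4.4.1 adds a comparison on its full 0-6 scale.

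**2. Can the proportion stand in for the mean?** Take three assumed distributions, with deaths at 0 as in SAP 3.1.7. Mean = Σ score × probability.

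| Arm | P(0) | P(20) | P(50) | P(80) | P(100) | Mean | P(≥95) |
|---|---|---|---|---|---|---|---|
| Reference | 0.20 | 0.10 | 0.15 | 0.15 | 0.40 | 0 + 2 + 7.5 + 12 + 40 = 61.5 | 0.40 |
| A | 0.10 | 0.05 | 0.15 | 0.30 | 0.40 | 0 + 1 + 7.5 + 24 + 40 = 72.5 | 0.40 |
| B | 0.20 | 0.15 | 0.15 | 0 | 0.50 | 0 + 3 + 7.5 + 0 + 50 = 60.5 | 0.50 |

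Arm A gains 11 points over the reference with no change at the cut. Arm B looks better at the cut and has a lower mean. One quantity cannot be read from the other.

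**3. Size on the 0-100 scale.** Assume 12% dead and 45% at ≥95 on placebo, with a common odds ratio (OR) across the scale.

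- P(≥95): odds 0.45/0.55 = 0.818. Multiplied by 2, 2.5 and 3, this gives 0.621, 0.672 and 0.711.
- P(dead): odds 0.12/0.88 = 0.136. Divided by 2, 2.5 and 3, this gives 0.064, 0.052 and 0.043.
- Crude hand check: put the top group at 100 and everyone between at 50. The placebo mean is 45 + 0.43 × 50 = 66.5. At OR 2 the middle group is 1 − 0.621 − 0.064 = 0.315, so the mean is 62.1 + 15.8 ≈ 77.8, a difference of about 11. The same steps give about 14.5 at OR 2.5 and 17 at OR 3.
- Spreading the middle 43% in three different assumed shapes gives roughly 10-14, 13-17 and 15-20 points.

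**4. Power.** Same assumptions, 33 per arm (100 over three arms), simulated unadjusted tests, with ranges over repeated runs and assumed shapes:

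| Common OR | Mean (t-test) | ≥95 (chi-square) | Rank test |
|---|---|---|---|
| 2 | about 30% | 32-33% | 32-34% |
| 2.5 | 44-46% | 47-51% | 51-53% |
| 3 | 57-59% | 61-63% | 65-67% |

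The cut at 95 is not less powerful than the mean under these assumptions. The planned model is covariate-adjusted, so these figures serve only to compare the tests.

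**The case against.** The strongest reply is that the SAP has done what SAPs are for. It chose a cut-point and a model, and the exception in 6.4 for analysis type and endpoint definition can be read to cover that. The choice is visible: 3.4.2 calls BI a dichotomised endpoint, and the version 3.0 history records an update to the Barthel analysis. The cut at 95 is a legitimate endpoint that costs no power on the figures above. BI ranks fifth in a safety trial. The internal conflict is one parenthesis in 2.1.2 (5), since 2.3.2 (5) is neutral.

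Most of that stands, and it rules out several stronger readings that a reader might reach:

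- *That ≥95 is the only planned use of BI, or that the mean will never be estimated.* Protocol 9.3.3 has a 0-100 analysis, though superseded. SAP 3.4.4.2 uses the full score, and SAP 3.1.4 could produce a by-arm mean and SD. Such a table is not specified for BI, but its absence is not established either.
- *That 6.4 denies any change.* The sentence carries its exception. The fair criticism is that moving from a 0-100 analysis to one cut changes the summary measure from a mean to an odds ratio, and 6.4 does not itemise it.
- *That the split wastes information the trial needs for power.* The illustration does not show this.

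The objection does not remove the mismatch between the SAP's own objective and its only between-arm BI comparison.

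**Conclusion.** The point holds in limited form. The governing SAP plans no between-arm comparison of mean Day 90 BI, although its own objective and the protocol define the outcome that way, and 6.4 does not list the substitution.

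The consequence is for interpretation. The ranked result does not answer the objective as worded, and the next trial is not assured an adjusted mean difference with an interval. That difference might be 10 to 20 points over common odds ratios of 2 to 3. This range rests on 12% dead, 45% at ≥95, proportional odds and three assumed shapes for the rest of the scale, none of them from the documents. No error-rate or power problem follows. This is a worthwhile improvement, not a threat to the trial's conclusions.

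**What to change.** 1. Keep BI ≥95 as the ranked test at items 5, 10 and 15.
2. Add to SAP 3.4.2 (5) a supportive Day 90 analysis on the 0-100 scale with death scored 0 as in 3.1.7. Report by-arm mean and SD, and the adjusted mean difference with a robust 95% CI for high dose, combined doses and low dose against placebo. Use the covariates already listed for BI, which include baseline BI and so address the synopsis wording. Robust standard errors are advisable because the score is bounded and piles up at both ends. State how missing scores are handled, because the existing rule of counting them as not independent does not carry over to a numeric score.
3. State in 2.1.2 (5) and 2.3.2 (5) that the proportion with BI ≥95 is the ranked quantity and the mean is supportive.
4. List the change from protocol 9.3.3 in 6.4.

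The cost is one extra model, one table and a few lines of text, with no new data. The added analysis sits outside the hierarchy, so the ranked tests are unaffected. If the team does not want a second analysis, items 3 and 4 alone (with 3 naming only the proportion) would remove the inconsistency, but the mean difference would remain unestimated.
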